7.8.2 Laboratory data

The analyses of laboratory data will be descriptive in nature and will follow BI standards (4).

Descriptive statistics for laboratory values will be displayed using the converted values in standard unit for data analyzed by the central laboratory. Shift tables of change in laboratory measurements between baseline and minimum, maximum or last value on treatment will be presented.

7.8.3 Vital signs

Only descriptive statistics are planned for this section of the report.

7.8.4 ECG

Clinically relevant abnormal ECG findings will be reported and analysed as AEs.

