#### **2.2.2.2      Further safety endpoints**

- Disease under study monitored using:
- PANSS total score and change from baseline
- Incidence of relapse
- SAS/BARS/AIMS Scale scores throughout the treatment
- Suicidality as assessed by C-SSRS
- Occurrence of protocol specified AESI
- Percentage of patients with (S)AEs (including clinically relevant abnormalities of physical examination, vital signs, ECG test and laboratory tests)

[REDACTED]

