#### **5.2.4      Electrocardiogram**

The 12-lead ECGs will be performed as scheduled in the [Flow Chart](#). Twelve-lead ECGs (I, II, III, aVR, aVL, aVF, V1 – V6) will be recorded using equipment provided by a central ECG vendor. The ECGs will be recorded for at least 10-second duration after the subjects have rested for at least 5 minutes in a supine position and prior to lab sampling. Electrode placement will be performed according to the method of Einthoven/Goldberger (ankles and wrists). At all time points indicated in the Flow Chart, single ECGs will be recorded. ECG recordings at planned time points may be repeated for quality reasons like alternating current artefacts, muscle movements and electrode dislocation. In this case the repeated ECG recordings will be used if quality was better.

The investigator or a designee will evaluate whether the ECG is normal or abnormal and whether it is clinically significant, if abnormal. The electronic version of the ECG is regarded as source data. Dated and signed printouts will be stored in the patient's medical file if there is no validated and certified e-medical record for ECG data.

Additional ECGs may be collected by the investigator for safety reasons. Clinically relevant findings noticed at Visit 1 should be reported as baseline condition.

Clinically relevant abnormal findings noticed after Visit 1 will be reported as AEs and followed up and/or treated locally until normal or stable condition.

All ECGs will be transmitted electronically to the central ECG vendor for centralized and independent evaluation tThe vendor will provide a report to the site. Abnormalities detected during this centralized ECG evaluation will not necessarily qualify as an AE. Decisions on eligibility for the trial are the responsibility of the investigator. Abnormalities detected in central evaluation must be reviewed by the investigator and if considered clinically significant reported as baseline condition if identified at Visit 1 or as adverse event if identified at or after Visit 2. All clinically relevant abnormal findings will be managed as medically appropriate, per investigators clinical judgment

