## **5.7 APPROPRIATENESS OF MEASUREMENTS**

All measurements performed during this trial are acceptable measurements and commonly used in monitoring safety aspects or assessing treatment response in patients with CIAS.

The scheduled measurements are appropriate to see drug induced changes in physical examination, vital signs, ECG and standard laboratory values. The primary and secondary efficacy endpoints and safety endpoints are standard and accepted for evaluation of safety and tolerability of an oral drug, and they are widely used in these kind of studies. The period of 26 weeks of treatment with Icleperitin is deemed appropriate to see a change in cognitive function in schizophrenic patients.

Therefore, the appropriateness of all measurements applied in this trial is given.

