Vital signs, physical examinations, or other safety-relevant data observed at screening, baseline, during the course of the trial and at the end-of-trial evaluation will be assessed with regard to possible changes compared to findings before start of treatment.

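### SAP 7.8.4 takes ECGs into the analysis only as investigator-judged adverse events, so the visible plan has no by-arm summary of the centrally evaluated ECGs that could show a modest QTc, PR or QRS shift

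*SAP*

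**What the plan says.** The ECG section of the SAP (7.8.4) is a single sentence: "Clinically relevant abnormal ECG findings will be reported and analysed as AEs". It shows no redaction.

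The protocol collects more than that sentence uses. The flow chart schedules a 12-lead ECG at Visits 1 and 2, at Weeks 6 and 12, and at end or early end of treatment. Protocol 5.2.4 specifies vendor equipment ("Twelve-lead ECGs (I, II, III, aVR, aVL, aVF, V1 – V6) will be recorded using equipment provided by a central ECG vendor") and central reading: "All ECGs will be transmitted electronically to the central ECG vendor for centralized and independent evaluation". The same section places a judgement between that reading and the database: "Abnormalities detected during this centralized ECG evaluation will not necessarily qualify as an AE", and "Abnormalities detected in central evaluation must be reviewed by the investigator and if considered clinically significant reported as baseline condition" if seen at Visit 1, or as an adverse event if seen at or after Visit 2.

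Three other protocol statements bear on the analysis:

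- Section 2.2.2.2 names ECG within one safety endpoint: "Percentage of patients with (S)AEs (including clinically relevant abnormalities of physical examination, vital signs, ECG test and laboratory tests".
- Section 5.7 gives the purpose of the schedule: "The scheduled measurements are appropriate to see drug induced changes in physical examination, vital signs, ECG and standard laboratory values".
- Section 7.2.5 says that vital signs, physical examinations and other safety-relevant data "will be assessed with regard to possible changes compared to findings before start of treatment". ECG is not named there.

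**The concern.** A blinded investigator looks at one patient at a time and asks whether a tracing matters for that patient. A small average lengthening of an interval in one arm does not show itself that way. It shows only when the readings are tabulated by randomised arm, and the visible SAP plans no such table for ECG.

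Every patient takes one or two background antipsychotics (protocol 3.3.2), and treatment lasts 26 weeks against 12 in phase II. The trial has a placebo arm and independently evaluated ECGs before and during treatment. Under the present plan, a report of few ECG adverse events would say little about a shift too small to prompt such reports.

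**Working it through.** **Step 1. What each type of safety measurement receives in the visible SAP.**

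| Measurement | Planned output | Visit-window table |
|---|---|---|
| Laboratory (7.8.2) | Descriptive statistics and shift tables against baseline | Table 6.7: 7 |
| Vital signs, including pulse rate (7.8.3) | Descriptive statistics | Table 6.7: 8 |
| Ophthalmologic variables (7.9) | Change from baseline and shift tables | Table 6.7: 9 |
| ECG (7.8.4) | AE tables only | None |

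The SAP's list of tables contains no ECG window table either, so redaction does not explain its absence. The AE groupings in SAP 7.8.1 cover abuse potential and CNS depression, ocular events, anaemia, drowsiness and sleep disorder. None gathers QT-related or arrhythmia terms, so such events would be counted under separate preferred terms.

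**Step 2. What a by-arm table could resolve.** There is no stated figure to reproduce, because the plan gives none for ECG. The patient numbers are from protocol 7.5: 293 randomised and 220 evaluable per arm. The SD of QTc change is an assumption, 15 to 25 ms.

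95% half-width of the arm difference in mean change = 1.96 × SD × √(2/n)

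- n = 293: 1.96 × √(2/293) = 0.162 SD
- n = 220: 1.96 × √(2/220) = 0.187 SD

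| Assumed SD | n = 293 | n = 220 |
|---|---|---|
| 15 ms | 2.4 ms | 2.8 ms |
| 20 ms | 3.2 ms | 3.7 ms |
| 25 ms | 4.1 ms | 4.7 ms |

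On these assumptions, data already being collected could show or exclude a mean shift of about 5 to 10 ms.

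**Step 3. What AE counts might show for the same shift.** Assume on-treatment QTc is normal with mean 410 ms and SD 20 ms, one reading per patient and 293 patients in the arm. Expected count above a cut = 293 × P(Z > (cut − mean)/20).

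| Cut | No shift (mean 410) | 10 ms shift (mean 420) |
|---|---|---|
| > 450 ms | z = 2.0: 6.7 | z = 1.5: 19.6 |
| > 480 ms | z = 3.5: 0.07 | z = 3.0: 0.40 |
| > 500 ms | z = 4.5: 0.001 | z = 4.0: 0.009 |

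If investigators report only readings above 480 ms, less than one patient is expected in either arm and the AE tables show nothing. If some report from 450 ms, part of the difference between about 7 and 20 patients could appear. Protocol 5.2.4 sets no threshold, so what the AE route would show depends on an unknown reporting habit. A categorical table does not depend on it.

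**The case against.** Several points on the other side stand.

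- **Heart rate.** A reader might infer that an effect on heart rate would go unseen. It would not. Pulse rate is a vital sign (protocol 5.2.2), is scheduled at the same treatment visits as the ECG, and is summarised under SAP 7.8.3.
- **Conflict with the protocol.** A reader might infer that the SAP silently dropped a promised analysis, since SAP Section 4 lists no ECG change. The documents do not support this. The endpoint in protocol 2.2.2.2 counts clinically relevant ECG abnormalities as adverse events, and the SAP does the same. Section 7.2.5 does not name ECG and prescribes no interval table; section 5.7 concerns the suitability of the measurements and commits to no analysis.
- **ECGs left unexamined.** This too would go too far. Every ECG is assessed by the investigator and centrally, central abnormalities must be reviewed, and adverse events are tabulated by arm. The data monitoring committee sees unblinded safety data, although the documents do not say whether that includes ECG intervals.
- **Prior evidence.** Protocol 1.2.5 reports no clinically relevant ECG findings, and the risk table in 1.4.2 lists no cardiac risk for the study drug. This lowers the expected yield. It does not show that a modest shift is absent over 26 weeks on background antipsychotics.
- **Feasibility.** Protocol 5.2.4 says that the vendor reports to the site. It does not say that interval measurements reach the sponsor.

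None of these supplies a by-arm view of QTc, PR or QRS.

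**Conclusion.** The point holds as a gap in descriptive safety reporting. In the visible SAP, ECGs enter the analysis only after an investigator's judgement, and nothing compares the central evaluations with baseline by arm. The SAP is consistent with the protocol's ECG endpoint, but it does not use the ECGs for the purpose given in protocol 5.7, nor carry the general wording of 7.2.5 through to them. What could be missed is a shift in QTc, PR or QRS too small to prompt many AE reports; a large effect could still surface in the AE tables.

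The size is illustrative. The half-widths of 2.4 to 4.7 ms rest on an assumed SD of 15 to 25 ms, and the expected counts on an assumed normal QTc distribution with one reading per patient. The documents give neither. No efficacy conclusion or error rate is affected. This is an inexpensive improvement and should be made if the data can be obtained.

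**What to change.** Extend SAP 7.8.4 with descriptive output from the central ECG evaluation, by arm:

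1. Value and change from the last pre-dose ECG, by visit, for QTcF, PR and QRS.
2. Counts of patients with new on-treatment QTcF above 450, 480 and 500 ms, and with increases above 30 and 60 ms, as descriptive categories only.
3. A shift table of the overall central reading (normal or abnormal) against baseline.
4. An ECG visit-window table in SAP 6.7, built on the scheduled ECG visits (Weeks 6, 12 and 26) and limited to the on-treatment period. Table 6.7: 8 should not simply be copied, because it sets its intermediate visits at Weeks 9 and 18.

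Keep clinically relevant findings as adverse events. If interval data are not transferred from the vendor, present the shift table alone and say so. If the sponsor prefers no ECG tables, a sentence giving the reason would close the point.

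The cost is SAP wording, a few tables and possibly a vendor data transfer. No extra ECGs, patients or hypothesis tests are needed.

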7.9 OTHER ANALYSES

Population pharmacokinetic and pharmacokinetic/pharmacodynamic analyses

A population PK analysis for iclepertin may be performed. Data of this study may be pooled with data of other iclepertin trials. Population PK and PK/PD analyses will be subject to a separate analysis plan(s) and report(s), and will not be part of the CTR.

Ophthalmologic variables

Each ophthalmologic variable is measured for both the right eye and the left eye. For continuous variables, summary statistics including mean, median, standard deviation, minimum, maximum will be presented for the change from baseline measurements.

[figure not shown]
For categorical variables, shift tables will be presented for the categorical changes from baseline.

[figure not shown]
8. TIMEPOINT OF RELEASE OF TREATMENT INFORMATION

[figure not shown]
The treatment information will be released to unblind the trial database after the last patient has completed their End-of-Study/Follow-up visit and all data has been entered and cleaned as defined in the “Data Ready to be Unblinded and/or Final Trial Closure Notification” (RUN) form.

[figure not shown]

11. HISTORY TABLE

Table 11: 1 History table

Version	Date (DD-MMM- YY)	Author	Sections changed	Brief description of change
2	25-OCT-24	[REDACTED]	Table 7.8.1: 2	This table was updated to fix a truncation issue in the previous version.
